All tests will be two-sided, p-values of less than 0.05 will be considered as evidence of a difference between treatment arms, and conditional effects will be reported. P-values will be reported to four decimal places with p-values less than 0.0001 as <0.0001. All confidence intervals presented will be 95% and two-sided. Exact confidence intervals will be used for binary data, where exact models have been used. Multiple comparisons will be performed and this may increase the probability of observing a statistically significant result by chance. No adjustments will be made to account for multiple testing. The statistical package SAS will be used to conduct analyses.

The key demographics and clinical condition of the participants will be presented for each arm of the trial to describe the cohort. In addition, a summary of transplant characteristics will be presented for each arm of the trial. A CONSORT diagram will be presented to show how participants progressed through the trial.

All analyses and accompanying tables will be presented by the treatment to which the participant was randomised. All odds, hazard and rate ratios will be presented as Plasmalyte arm versus Standard arm. A ratio which is greater than 1 indicates that the odds, hazard or rate of the event is greater in the Plasmalyte arm. 95% confidence intervals will be presented with all ratios.

P-values for regression models will be obtained by comparing models with and without the treatment term using the likelihood ratio test. In analyses where mixed models are performed, the log-likelihood will be estimated using pseudo-likelihood methods.

All analyses will be adjusted for the stratification variables (site and participant weight pre transplant: <20kg and ≥20kg) and donor type: deceased and living, as this was also felt to be an important factor which could affect the outcomes of interest. Site will be

Statistical Analysis Plan

accounted for by including a random effect and participant weight and donor type by a fixed effect in each model.

Although PLUTO is a definitive trial, the total sample size is relatively small, hence:

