- Hypomagnesaemia (defined as plasma magnesium concentration < 0.7 mmol/L)
- Hyperchloraemia (defined as plasma chloride concentration > 107mmol/L)
- Excessive rate of reduction in plasma sodium concentration (defined as >1mmol/L/hour averaged over 6 hours)
- Excessive magnitude of reduction in plasma sodium concentration (defined as > 10mmol/L from pre-transplant level)

The number and percentage of participants who experience each of these events will be presented by trial arm and overall, alongside the median and interquartile range of the number of each event experienced. To test for differences in the proportion of participants experiencing each event, separate mixed logistic regression models will be used. These will be adjusted for donor type (living vs deceased donor), participant weight (<20kg vs ≥20kg pre-transplant) and transplant centre as a random effect. The adjusted odds ratio for treatment, with 95% confidence interval, will be presented from this model, with the p-value from the likelihood ratio test when including and excluding the treatment term from the model.

Maximum and minimum systolic blood pressure

The minimum and maximum systolic blood pressure will be taken for each day, for the first 3 days post-transplant (the measurement recorded in the database will have been sustained on 3 repeated values on each day). The values will be normalised to age and height percentile by the statistician, using the process as specified in https://www.nhlbi.nih.gov/files/docs/resources/heart/hbp ped.pdf and

Statistical Analysis Plan

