https://www.who.int/toolkits/growth-reference-data-for-5to19-years will be used to determine the height percentiles. Heights in cm will be converted to inches by dividing by 2.54 and will utilise the height at transplant. The mean minimum and maximum normalised systolic blood pressure, with standard deviation, will be presented separately for each trial arm and overall, for each day. A repeated measures mixed Normal linear regression will be used to assess whether mean percentiles over the three days are different between the two treatment arms, adjusting for donor type (living vs deceased donor), participant weight pre transplant (<20kg vs ≥20kg pre-transplant) and day of measurement. In addition, two random effects will be included in the model to account for individual participant effects and transplant centre. Residual plots from the normal linear regression will be examined. If there is any evidence of skew or non-constant variance, repeated measures mixed normal linear regression of log-transformed percentile will be used to assess whether mean log-percentile are different between the two treatment arms, adjusting for donor type (living vs deceased donor), participant weight pre transplant (<20kg vs ≥20kg pre-transplant) and participant and transplant centre as random effects.

Number of changes in intravenous fluid composition within the first 72 hours post-transplant

A change to intravenous fluid composition will be defined as any modification to the composition of the fluid administered to the participant. The number of changes in fluid will be counted as follows:

- If the participant is initially given something different to which they were randomised, this will be counted as the first change
- Subsequent changes will be counted based on the fluid being administered before the change.
- Diluent used for drug infusions, will not be counted.

For example:

- if the participant was randomised to standard arm, was first administered Hartmann's solution, then 0.9% sodium chloride, and then Hartmann's solution again, this would be counted as two changes.
- If the participant was randomised to Plasma-Lyte, was first administered 5% glucose, then received Plasma-Lyte 148 and then Plasma-Lyte® 148 & Glucose 5%, this would count as three changes.

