3.8 Procedures for handling Missing Data

Any missing primary and secondary outcome data will be summarised. For the primary outcome and other blood test results, the result will be considered missing if there are no results for that measurement within the 72-hour period post transplant. It is anticipated that missing data for the primary outcome will be rare, as the plasma sodium measurement is also used to determine one of the key SAEs within the trial, which mandates immediate reporting. Missing data due to death or withdrawal are also anticipated to be very rare: data from the UKTR showed that the 1-year patient survival rate for those transplanted between 2015-2018 was 99% (95% confidence interval 96-100) for paediatric kidney transplants from living and DBD donors (5). Primary and secondary outcome measures will not be imputed and these will be treated as missing data and excluded from the relevant analyses. If outcome data is missing for more than 25% of participants, outcomes will not be reported.

To explore if missing values have an undue impact on the primary outcome result, a sensitivity analysis using multiple imputation will be performed if the primary outcome is missing in more than 5% of the participants included in the modified intention to treat analysis. Variables will be included in the imputation model if they have a completeness of ≥65% and these variables are:

- Donor: type, age, ethnicity, BMI
- Trial participant/Recipient: age, sex, ethnicity, cause of end stage kidney disease, native urine output, dialysis type, weight and height at transplant, systolic blood pressure, blood group, calculated reaction frequency, graft number
- Transplant: blood group match, transplanting centre, cold ischaemic time, HLA mismatch between donor and recipient, graft placement.

Forty imputations will be used and the average across the imputations will be calculated. The model specified in section 3.3 will be utilised.

If the proportion of participants with a missing primary outcome is less than or equal to 5% then this sensitivity analysis will not be performed.

Statistical Analysis Plan

All the risk adjustment factors will always be known, as weight and site are required for randomisation and donor type is mandatory data required by the UKTR.

4. Data Analysis Tables

Data analysis will be based on the following tables.

- 4.1 Screening, Recruitment and Follow-up tables
 - 4.1.1 Recruitment by Centre

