4.1.5 Protocol Deviations

| Table XX Protocol deviations | | | | | | |
|------------------------------|----------------------|---|------------------------------------|----------------------------|--|--|
| Randomisation number | Randomised treatment | Description of and reason for deviation | Clinical significance of deviation | Included in mITT analysis? | | |
| | | | | | | |
| | | | | | | |
| | | | | | | |
| mITT = modified | I intention to treat | t (primary analysis po | oulation) | | | |

| Table XX Summary of withdrawn, randomised in error, co-enrolled and protocol deviations n (%) | | | | | | |
|---|----------------------------|----------------------|------------|--|--|--|
| | Standard care (n=) | Plasma-Lyte 148 (n=) | Total (n=) | | | |
| Withdrawn* | | | | | | |
| Randomised in error | | | | | | |
| Co-enrolled | | | | | | |
| Protocol deviations | | | | | | |
| Randomised but not transplanted | | | | | | |
| *Excludes cases which w | vere randomised but not tr | ansplanted. | | | | |

Statistical Analysis Plan

4.2 **Baseline Characteristics tables**

| | Randomise | | |
|--------------------------------------|--------------------|----------------------|------------|
| Participant characteristic | Standard care (n=) | Plasma-Lyte 148 (n=) | Total (n=) |
| Age (years) | | | |
| Male | | | |
| Ethnicity | | | |
| Asian | | | |
| Black | | | |
| Mixed | | | |
| White | | | |
| Other | | | |
| Unknown | | | |
| Cause of end stage kidney disease | | | |
| Tubulointerstitial disease | | | |
| (CAKUT/non-CAKUT) | | | |
| Glomerular disease | | | |
| Hereditary nephropathies | | | |
| Systemic diseases | | | |
| Other | | | |
| Native urine output (ml/kg/24 hours) | | | |
| Dialysis type | | | |
| Haemodialysis | | | |
| Peritoneal dialysis | | | |
| Pre-emptive (no dialysis) | | | |
| Patient weight at transplant (kg) | | | |
| Patient height at transplant (cm) | | | |
| BMI (kg/m²) | | | |
| Systolic blood pressure ¹ | | | |
| Blood group | | | |
| 0 | | | |
| A | | | |
| В | | | |
| AB | | | |
| Recipient waiting time in days (if | | | |
| deceased donor transplant) | | | |
| cRF ² (%) | | | |
| Graft number | | | |
| First | | | |
| Second | | | |

Summary of missing data:

Statistical Analysis Plan

| | Randomise | d Treatment | |
|--|------------------------|--------------------------|----------------|
| | Standard care (n=) | Plasma-Lyte 148 (n=) | Total (n=) |
| Cold ischemia time (hours)* | , | , , | |
| Deceased donor | | | |

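### The systolic blood pressure models do not adjust for pre-transplant systolic pressure, although the trial collects it, so a secondary comparison is less precise than it need be

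*SAP*

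**What the plan says.** The outcome is defined in SAP section 3.4, in the part on extremes of systolic pressure, as follows: "The minimum and maximum systolic blood pressure will be taken for each day, for the first 3 days post-transplant". The values are then normalised to age and height percentiles.

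The analysis is a repeated-measures mixed Normal model "to assess whether mean percentiles over the three days are different between the two treatment arms, adjusting for donor type". The other fixed effects are "participant weight pre transplant (<20kg vs ≥20kg pre-transplant) and day of measurement", and "two random effects will be included in the model to account for individual participant effects and transplant centre". If residuals are skewed or their variance is not constant, the same comparison is made on log-transformed percentiles. That fallback has no baseline term either.

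The general rule in section 3.2 is "All analyses will be adjusted for the stratification variables (site and participant weight pre transplant: <20kg and ≥20kg) and donor type". The footnote to the systolic pressure table in section 4.4 names the same three factors: site, weight group and donor type.

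A recipient systolic pressure is nevertheless held. Section 4.2 has a baseline row labelled "Systolic blood pressure". Section 3.8 lists it among the recipient variables for multiple imputation of the primary outcome: "weight and height at transplant, systolic blood pressure, blood group". The SAP gives no reason for leaving it out of the systolic pressure models.

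**The concern.** A pre-treatment measurement of the same physiological variable is usually among the better predictors of a continuous outcome. Leaving it out costs precision and leaves any chance difference between arms in starting pressure uncorrected.

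The terms already in the model do not do this work. The participant random effect gives the right standard error for three correlated readings per child, but it does not use the baseline value to explain why children differ, and it does not remove a baseline difference between arms. Normalisation for age and height, and a two-level weight group, do not do so either.

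The omission also sits oddly with the plan's own reasoning. Section 3.2 adds donor type, which is not a stratification factor, because it may affect the outcomes. Baseline pressure meets that test at least as well. Two other outcomes in section 3.4 are measured from a pre-transplant value: fluid overload (from weight) and excessive fall in sodium.

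At stake are the width of the interval for two secondary contrasts, and how far those contrasts depend on the luck of the allocation. If the covariate is not fixed in advance, there is also a temptation to adjust later because the baseline table looks uneven.

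**Working it through.** The SAP gives no SD, correlation, target difference or power for systolic pressure, so there is no stated figure to reproduce. Every correlation below is an assumption, shown over a range.

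**Inputs from the SAP.** 144 children randomised 1:1, 128 before the drop-out allowance (section 1.6); three daily values per child (section 3.4); a 65% completeness threshold for variables entering the imputation model (section 3.8).

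**Step 1: variance.** With three values per child and a participant random effect, the treatment contrast is in essence the difference between arms in the 3-day mean. Let ρ be the correlation of baseline with that mean after the existing covariates. Adding baseline multiplies the variance by 1 − ρ² and the interval width by √(1 − ρ²).

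| ρ | Variance reduction | Interval narrower by |
|---|---|---|
| 0.3 | 9% | 1 − √0.91 = 5% |
| 0.5 | 25% | 1 − √0.75 = 13% |
| 0.7 | 49% | 1 − √0.51 = 29% |

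A hypothetical effect with 80% power unadjusted would have power Φ(2.80/√(1 − ρ²) − 1.96), which is 84%, 90% and 98% in the three rows. The 80% starting point is only a scale for reading the gain. It is not a property of this plan.

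**Step 2: the same check with single-day correlations.** Let r be the correlation between any two post-transplant days and b the correlation of baseline with a single day. The variance ratio is 1 − b²/[(1 + 2r)/3].

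- b = r = 0.3, 0.5, 0.7: ratios 0.83, 0.63, 0.39; interval narrower by 9%, 21%, 38%.
- r = 0.6 with a weaker baseline link, b = 0.2, 0.3, 0.4: ratios 0.95, 0.88, 0.78; interval narrower by 3%, 6%, 12%.

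The two steps agree. At b = r = 0.5 the correlation with the 3-day mean is 0.5/√0.667 = 0.61, and 1 − 0.61² = 0.63.

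**Step 3: chance imbalance.** The difference between arms in mean baseline has a standard error of √(4/N) in SD units: 0.167 at N = 144 and 0.177 at N = 128. The unadjusted contrast moves by ρ times the imbalance. A 0.2 SD imbalance, about 1.2 standard errors at N = 144, moves it by 0.06, 0.10 or 0.14 SD of the 3-day mean at ρ = 0.3, 0.5 or 0.7.

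**Step 4: incomplete baseline.** With mean imputation plus an indicator, the variance reduction is roughly the observed fraction times ρ². At 65% complete it is 0.65 × 9% = 6% at ρ = 0.3 and 0.65 × 25% = 16% at ρ = 0.5. The 65% is an entry rule for the imputation model, not a forecast of how complete baseline pressure will be.

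**The case against.** The best case for the plan is that nothing in it is wrong. One adjustment rule is prespecified for all analyses and the systolic models follow it. Randomisation makes the contrast unbiased on average, and the planned interval already allows for chance imbalance. The outcome is secondary, and section 3.2 says only the primary outcome was powered. All of that stands, and it limits the point to efficiency.

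Three stronger readings might be inferred, and the SAP does not support them.

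- **That a baseline imbalance passes in full into the estimate.** It does not. It is scaled by the correlation, as in Step 3.
- **That the baseline reading is the same quantity as the outcome.** The outcome is a sustained daily extreme. The baseline row says only systolic pressure, and the text of its footnote could not be read in the copy used here, so its timing and its scale are not established.
- **That large power gains are available.** The larger figures need a strong correlation after surgery and fluid loading, complete baseline data, and little overlap with donor type, weight group and centre. The SAP shows none of these. At the weak end the interval narrows by only a few per cent.

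The objection does not show a benefit in leaving the covariate out. Even if the correlation is weak, the cost is one degree of freedom for baseline and one for the missing indicator.

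**Conclusion.** The point holds as a matter of precision. The maximum and minimum systolic models and their fallbacks omit a pre-treatment value that the trial collects, so their intervals are wider than the collected data allow whenever baseline predicts the outcome, and a chance imbalance shifts the estimate by ρ times its size.

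How much is lost cannot be settled from the SAP. It depends on an unstated correlation, on how complete the baseline readings are, and on how much the existing covariates already explain. A plausible span runs from a gain of a few per cent in interval width to something substantial. The planned analysis is valid without the change and the primary result is untouched. The change is still worth making because it is nearly free, and because fixing it before unblinded data are seen removes a later discretionary choice.

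**What to change.** In section 3.4, add pre-transplant systolic pressure as a fixed continuous covariate in the maximum model, the minimum model and the log-scale fallback of each. Normalise it to the age and height percentile in the same way as the outcome.

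State that a missing baseline value is replaced by the overall mean, with a missing indicator in the model, so that no child is dropped. State which reading serves as baseline.

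Two other places need matching edits: the adjustment footnote to the systolic pressure table in section 4.4, and the closing statement of section 3.8 that the adjustment factors are always known, which would no longer be true for this outcome.

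The cost is one covariate and one indicator in two models, plus three lines of text. Age and height at transplant are already recorded, so no new data collection appears to be needed, provided the baseline reading is recorded in a form that can be normalised.

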3.5 Other outcome measures

Investigation into acute hyponatremia and plasma sodium concentration

Time to first develop acute hyponatremia

This outcome will be measured from transplant operation start time ("knife to skin") till the first time the plasma sodium concentration drops below 135mmol/L. The maximum time will be 72 hours post-transplant and the time will be measured in hours. It will be estimated using competing risks analysis. Acute

Statistical Analysis Plan

hyponatremia will be considered as the event and death prior to the event will be considered as the competing risk. Median (IQR) time to first develop acute hyponatremia from the cumulative incidence curve will be reported for each trial arm and overall. Although if there are no deaths, the Kaplan-Meier method will be used. To accommodate a random centre effect and adjustment for participant weight and donor type, Cox regression analysis with a frailty term will be used to compare time to first develop acute hyponatremia between treatment arms. Participants who have not experienced the event by 72 hours will be censored at this point, as will any participants who die or were withdrawn prior to 72 hours post transplant. The estimate of the hazard of acute hyponatremia from this model should be interpreted with caution because it does not properly account for the competing risk of death. However, since the number of deaths is predicted to be small, the impact of the competing risk is likely to be negligible. This will be explored by examining the cumulative incidence function for death.

- Duration of acute hyponatremia For those participants who experience acute hyponatremia, the total time between transplant operation start time and 72 hours post-transplant when the participant's plasma sodium concentration is below 135mmol/L will be calculated in hours. The start time of an acute hyponatraemia event in this period will be taken as the time of the first test where plasma sodium is <135mmol/L. The corresponding end time will be the time of the first test after this where plasma sodium is ≥135mmol/L, or 72 hours post-transplant, whichever occurs first. For each participant, these event durations will then be totalled. The mean duration, with standard deviation, will be presented for each trial arm and overall. A Normal linear regression model will be used to assess whether mean duration is different between the two treatment arms, adjusting for donor type (living vs deceased donor), participant weight pre transplant (<20kg vs ≥20kg pre-transplant) and transplant centre as a random effect. Residual plots from the normal linear regression will be examined. If there is any evidence of skew or non-constant variance, normal linear regression of log-transformed duration will be used to assess whether mean log-duration are different between the two treatment arms, adjusting for donor type (living vs deceased donor), participant weight pre transplant (<20kg vs ≥20kg pre-transplant) and transplant centre as a random
- Magnitude of variation in plasma sodium concentration in first 72h For each participant, the difference between their maximum and minimum plasma sodium concentration between transplant operation start and 72 hours post transplant, will be calculated. This outcome is clinically important as variation leads to fluid shifts, brain oedema and seizures. The mean magnitude of variation, with standard deviation, will be presented for each trial arm and overall. A Normal linear regression model will be used to assess whether mean magnitude of variation is different between the two treatment arms, adjusting for donor type (living vs deceased donor), participant weight pre transplant (<20kg vs ≥20kg pre-transplant) and transplant centre as a random effect. Residual plots from the normal linear regression will be examined. If there is any evidence of skew or non-constant variance, normal linear regression of log-transformed magnitude of variation will be used to assess whether mean log- magnitude of variation are different between the two treatment arms, adjusting for donor type (living vs deceased donor), participant weight pre transplant (<20kg vs ≥20kg pre-transplant) and transplant centre as a random effect.
- Maximum rate of change of plasma sodium concentration in first 72h

(Template Version 07/10/08)

effect.

Statistical Analysis Plan

For each participant, all plasma sodium concentrations measurements which are ≥5mmol/l and which were taken between transplant operation start and 72 hours post-transplant will be compared. The rate of change will be calculated, for tests taken at least six hours apart, by taking the difference between the measurements and dividing by the number of hours between the measurements. The maximum decrease of these will be selected for each participant. The mean maximum rate, with standard deviation, will be presented for each trial arm and overall. A Normal linear regression model will be used to assess whether mean maximum rate is different between the two treatment arms, adjusting for donor type (living vs deceased donor), participant weight pre transplant (<20kg vs ≥20kg pre-transplant) and transplant centre as a random effect. Residual plots from the normal linear regression will be examined. If there is any evidence of skew or non-constant variance, normal linear regression of log-transformed maximum rate will be used to assess whether mean log- maximum rate are different between the two treatment arms, adjusting for donor type (living vs deceased donor), participant weight pre transplant (<20kg vs ≥20kg pretransplant) and transplant centre as a random effect.

Serious adverse events

Serious adverse events will be tabulated by classification (Acute severe hyponatraemia – symptomatic and non-symptomatic (separately), severe hyperkalaemia, seizures and other) and treatment arm. The number of participants who experienced at least one SAE will also be presented. Following the implementation of protocol v2.0, SAEs relating to electrolytes were no longer required to be reported by sites. Therefore, both acute severe hyponatraemia and severe hyperkalaemia will also be identified through all participants' plasma and blood gas results, including those SAEs which occurred prior to the protocol change. Acute severe hyponatraemia is defined as: a fall in plasma or blood gas sodium concentration of ≥10mmol/L from the pre transplant level or a rate of fall of plasma or blood gas sodium concentration exceeding 1mmol/L/hour averaged over 6 hours. A plasma or blood gas potassium concentration >6.5mmol/L will be used to identify acute severe hyperkalaemia. No statistical testing will be conducted.

Graft and patient survival at 90 days

This outcome will be measured from transplant operation date till 90 days post transplant, measured in days and the Kaplan-Meier method will be used to separately to estimate the graft and patient survival at 90 days with 95% confidence interval. For graft survival, deaths will be censored and graft failure will be considered as the event. For patient survival death will be considered as the event. No statistical testing will be conducted.

Volume of intravenous fluid received

A summary of the volume of intravenous fluid received will be presented, by treatment arm and overall. The total intravenous fluid volume received overall and by fluid type, will also be tabulated. No statistical testing will be conducted.

Medication and blood products

A summary table showing the medication and blood products received will be compiled by treatment arm. No statistical testing will be conducted.

Statistical Analysis Plan

Primary outcome events confirmed by additional blood gas

For the primary outcome it was specified, where feasible, a concurrent blood gas should be performed to confirm the result, although this was not compulsory. Confirmatory blood gas sodium measurements should be +/-30mins from lab sample taken at the onset of event. The number of primary outcome events confirmed by a blood gas result will be tabulated by treatment arm and overall, with percentages.

